4.5. Handling Data From Patients Withdraw and Re-Enter the Study

Patients who terminate early from the study due to emergency circumstances (such as coronavirus disease 2019 [COVID-19]) may be allowed to re-enter the study at a later date. Patients re-entering the study will be manually assigned to their initial treatment group and will redo the entire study from the start.

4.5.1. Baseline Values

In general, baseline values from the re-entered participation will be used. Missing baseline values will be handled in the same method as other non-withdrawal patients.

The blinded CYP2D6 genotyping is the only measurement that is not required for re-entering patients. Results from the original participation of the CYP2D6 impairment status at baseline will be carried over to the repeated participation (re-entered) portion.

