2. STUDY DESIGN

2.1. General Design

This is a Phase 3, 21-week, multicenter, randomized, double-blind, placebo-controlled, parallel group study to evaluate the efficacy and safety of TEV-50717 administered as oral tablets at a starting dose of 6 mg once daily in patients (age 6 through 18 years, inclusive) with DCP with predominant choreiform movement disorder, who have had cerebral palsy (CP) symptoms, of a non-progressive nature, since infancy (≤ 2 years of age).

The study will consist of a screening period (up to 31 days) and a double-blind treatment period including a titration period (7 weeks) and a maintenance period (8 weeks), followed by a washout period of 1 week, and a follow-up telephone contact 1 week after the washout period.

At the baseline visit (day 1), patients will be randomly assigned to 1 of 2 treatment groups with TEV-50717 IMP or placebo IMP in a 2:1 ratio stratified by age at baseline (6 to <12 years; 12 through 18 years, inclusive) and region (US; non-US).

Titration period (7 weeks): The titration scheme and maximum dose will be determined by body weight and cytochrome P450 2D6 (CYP2D6) impairment status at baseline¹; patients will be classified as CYP2D6 impaired if they are receiving a strong CYP2D6 inhibitor or are a CYP2D6 poor metabolizer. IMP will be titrated during the double-blind treatment period starting with 6 mg of TEV-50717 or matching placebo IMP. During the titration period, patients and their caregiver/adult will interact weekly with the investigator/staff from week 1 through week 7: in-person (in-clinic) study visits will be scheduled at weeks 3 and 7, and telephone contacts (with non-recording live video) will be scheduled for weeks 1, 2, 4, 5, and 6 in order to assess dyskinesia and adverse events. The telephone contacts to the patient will be supported by live video stream, without recording, to provide visual confirmation to the investigator of the verbal information provided by the patient or caregiver. The dose of IMP will be adjusted according to the titration scheme to identify a dose level that optimally reduces dyskinesia (as determined by the investigator) and is well tolerated. If a patient experiences a “clinically significant” adverse event attributable to the IMP, the investigator will first determine if a dose reduction (to the previous dose level) or suspension is necessary and possible.

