4. GENERAL ISSUES FOR DATA ANALYSIS

4.1. General

Descriptive statistics for continuous variables include number (n), mean, standard deviation (SD), standard error (SE), median, minimum, and maximum. Mean, SD and SE will not be presented if the number of patients in the analysis is less than 5 ($n < 5$).

Descriptive statistics for categorical variables include patient counts and percentages. Missing category will be displayed as appropriate.

The following variables are used as stratification factors for randomization or determination of titration scheme and maximal dose: CYP2D6 impairment status; weight category; age group; region. For the purpose of analysis, the actual baseline values as derived from the Case Report Form (CRF), or from the CRF and the laboratory database in case of CYP2D6 impairment status, will be used in the case of discrepancy between Randomization and Trial Supply Management (RTSM) and CRF data.

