5.3. Demographics and Baseline Characteristics

Patient demographic and baseline characteristics will be summarized using descriptive statistics.

The continuous variables of patient age, weight, height, and body mass index (BMI) will be summarized using descriptive statistics.

BMI at baseline will be computed as:

$$\text{BMI (kg/m}^2\text{)} = \text{Weight at baseline (kg)} / [\text{Height at screening (m)}^2].$$

Height, weight, and BMI at baseline will also be presented by age group and sex using descriptive statistics. In addition, normal age and sex-based z-scores and percentiles for BMI will be determined using the World Health Organization (WHO) growth charts, and summarized descriptively.

The categorical variables of patient weight group, sex, race, ethnicity, and region (United States (US) and non-US) and country for non-US will be summarized using descriptive statistics for each category. The categorical variables of age group at baseline (6 to <12 years, 12 through 18 years, inclusive), use of a strong CYP2D6 inhibitor, as appears in Table 9 of the study protocol (Yes/No), CYP2D6 genotype (Poor CYP2D6 metabolizer/ Non-poor CYP2D6 metabolizer), and CYP2D6 impairment status (Impaired/Not impaired) will be summarized using descriptive statistics for each category. In addition, age and sex-based BMI categories include: Underweight (< 5 percentile), Normal (≥ 5 - < 85 percentile), Overweight (≥ 85 - < 95 percentile), Obese (≥ 95 percentile), will be tabulated for each category.

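### Section 4.5.1 carries over the composite CYP2D6 impairment status at re-entry, although only its genotype component is fixed

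*SAP*

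**What the plan says.** SAP Section 2.1 defines the status by two alternatives: "patients will be classified as CYP2D6 impaired if they are receiving a strong CYP2D6 inhibitor or are a CYP2D6 poor metabolizer". It also ties the titration scheme and the maximum dose to this status at baseline.

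Section 4.1 addresses discrepancies between RTSM and CRF data. In that case the actual baseline values are taken from the CRF, "or from the CRF and the laboratory database in case of CYP2D6 impairment status". Section 5.3 lists strong-inhibitor use, CYP2D6 genotype and CYP2D6 impairment status as three separate baseline variables.

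Under Section 4.5, a patient who re-enters keeps the first treatment assignment and "will redo the entire study from the start". Section 4.5.1 then gives three rules:

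- The general rule: "In general, baseline values from the re-entered participation will be used".
- The exception for measurement: "The blinded CYP2D6 genotyping is the only measurement that is not required for re-entering patients".
- The carry-over: "Results from the original participation of the CYP2D6 impairment status at baseline will be carried over to the repeated participation (re-entered) portion".

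Sections 4.5.2 and 4.5.3 put only the repeated participation into the summaries and analyses.

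**The concern.** The exception for measurement covers the genotype, which does not change and so need not be repeated. The carry-over sentence that follows names a different variable, the composite status. One component of that composite, strong-inhibitor use, can change between the two participations.

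A programmer who follows the sentence as written attaches the status from the first participation to data that come only from the second. Inhibitor use, under the general rule of 4.5.1, comes from the re-entry baseline. The two variables can then disagree for the same patient in a way that the definition in 2.1 rules out.

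What is at stake is the correctness of descriptive tables that use the status, and the consistency of a variable that 2.1 also links to the titration scheme.

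**Working it through.** The SAP gives no figure to reproduce on this point. The check sets the rules against each other and enumerates the cases.

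**Inputs.** Definition of the status: Section 2.1. Carry-over rule and general baseline rule: Section 4.5.1. Uses of the status: Sections 5.3, 5.7 and 6.4. Model terms: Sections 6.2.3 and 6.3.1.1.

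**Step 1: rule by rule.** By 2.1, status = poor metabolizer OR strong inhibitor at baseline. For a re-entering patient the relevant baseline is the re-entry one (4.5.1, general rule). The literal carry-over instead gives status = poor metabolizer OR strong inhibitor at the first baseline.

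**Step 2: enumeration.** There are 2 genotypes × 2 states of inhibitor use at the first baseline × 2 at re-entry = 8 combinations.

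| Genotype | Inhibitor, first baseline | Inhibitor, re-entry | Carried-over status | Status by 2.1 at re-entry | Agree? |
|---|---|---|---|---|---|
| Poor | Yes | Yes | Impaired | Impaired | Yes |
| Poor | Yes | No | Impaired | Impaired | Yes |
| Poor | No | Yes | Impaired | Impaired | Yes |
| Poor | No | No | Impaired | Impaired | Yes |
| Non-poor | Yes | Yes | Impaired | Impaired | Yes |
| Non-poor | No | No | Not impaired | Not impaired | Yes |
| Non-poor | Yes | No | Impaired | Not impaired | **No** |
| Non-poor | No | Yes | Not impaired | Impaired | **No** |

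Two of 8 combinations are misclassified, both in non-poor metabolizers whose inhibitor use changed. This counts logical cases and does not estimate a rate. If only the genotype is carried over and the status is derived at re-entry, 0 of 8 are misclassified. In the last row the baseline table would show inhibitor use as present and status as not impaired.

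**Step 3: where the label enters.**

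- Baseline characteristics (5.3).
- Weekly dose level by weight group and status, and maintenance dose as a percentage of the maximal planned dose (5.7). The week 7 rows of Tables 4 and 5 give maxima, non-impaired versus impaired, of 24 versus 12, 30 versus 18, 42 versus 24 and 48 versus 36 mg/day across the four weight groups. For example, 24 mg in the 30 to <40 kg group is 24/42 = 57% of one maximum and 24/24 = 100% of the other. The label moves this percentage only if the planned maximum is looked up from it.
- The CYP2D6 subgroup (6.4), which is descriptive. If the smaller subgroup has fewer than 5 patients, the main analysis is repeated on the larger one, so the label also determines who is in that repeat.

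**Step 4: where it does not enter.** The primary model adjusts for the baseline score, age group and region, and its imputation models use these plus the week 9 and week 12 scores. The key secondary models follow the same pattern with their own baseline covariate. None contains CYP2D6 status.

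**The case against.** The strongest reply is that only the genotype was meant. The carry-over sentence comes straight after the one on genotyping and speaks of results, which suits a laboratory result. Inhibitor use would then fall under the general rule and be taken afresh. This is a plausible account of the intention, but the sentence names a variable that 5.3 lists separately from genotype, and nothing in the SAP tells the analyst to re-derive it.

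A second reply is that Section 4.1 already points to actual baseline values. It does so only where RTSM and CRF data disagree, and 4.5.1 is the more specific rule for re-entering patients. The SAP does not say which governs.

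A third reply is that the protocol, not shown here, may restrict inhibitor changes or handle the case. It may, and that bears on how often the problem arises. For the analysis, however, the SAP's introduction says that the SAP prevails where the two differ.

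The argument on size stands. The status is outside all confirmatory models. An error needs a patient who re-entered, is a non-poor metabolizer and changed strong-inhibitor use in between.

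A reader might also infer that such patients were dosed under the wrong scheme. The SAP does not support that: 4.5.1 is a data-handling rule, and the document does not show how re-entering patients were titrated. Nor can both harms be claimed for the same patient. If the carried-over status also set the dosing scheme, a dose summary by that status describes the scheme actually assigned. If dosing used a newly derived status, only the analysis label is wrong.

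**Conclusion.** The conflict is real but narrow. As written, 4.5.1 carries over a composite of which only the genotype is fixed, and it gives a re-entering non-poor metabolizer with changed inhibitor use a status that contradicts 2.1 and the derivation in 4.1. The consequence is limited to the baseline table, the titration and maintenance-dose summaries and the CYP2D6 subgroup. The primary and key secondary results are unaffected.

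The conclusion assumes that the sentence is programmed literally. The SAP states neither the number of re-entering patients nor how often inhibitor use changes, so the number affected is unknown and may be zero. For the same reason, it cannot be claimed that one or two errors would decide whether the 5-patient threshold in 6.4 is met, because the SAP gives no share of impaired patients to support it.

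**What to change.** In Section 4.5.1, limit the carry-over to the CYP2D6 genotype result. State that, for analysis, the baseline impairment status of a re-entering patient is derived from that genotype plus strong-inhibitor use recorded at the re-entry baseline, as 2.1 and 4.1 define it.

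Because 2.1 also links the titration scheme and maximum dose to this status, Sections 2.1, 4.1 and 4.5.1 must be reconciled so that one definition applies throughout. No dosing rule is proposed here.

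The cost is one sentence in the SAP and a short derivation. No new assessment is needed: Section 5.6 already has medication from the 3 months before baseline recorded on the CRF, and a re-entering patient repeats the study from the start.

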4.5.2. Efficacy Data

For each patient that re-entered the study, only data from the repeated participation will be included in the ITT, mITT, PP, mITTA, and mITTB analysis sets. The original participation data will be listed separately and will not be included in any summary tables or statistical analysis.

Missing postbaseline efficacy values will be handled in the same method as other non-withdrawal patients.

4.5.3. Safety Data

For each patient that re-entered the study, only data from the repeated participation will be included in the ITT and safety analysis sets. The original participation data will be listed separately and will not be included in any summary tables. In case of a SAE that occurred during the original participation and resolved prior to re-entering, the SAE will be documented in medical history database. Missing postbaseline safety values will be handled in the same method as other non-withdrawal patients.

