3.3. Safety Analysis Set

The safety analysis set will include all randomized patients who receive at least 1 dose of IMP.

In the safety analysis set, treatment will be assigned based on the treatment patients actually received, regardless of the treatment to which they were randomized, unless otherwise specified.

Rules for assignment of treatment in case of mixed actual treatments:

- If a patient received placebo throughout the entire treatment period, then actual treatment is placebo.
- If a patient was randomized to placebo and received TEV-50717 for up to 7 days, then actual treatment is placebo
- Otherwise, actual treatment is TEV-50717.

For patients who discontinue the study and re-enter it (repeating the study from baseline; see Section 4.5) only the data from the repeated participation will be included in the safety analysis set.

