8.3. Adverse Events

Adverse events will be collected and recorded from the time a patient signs the informed consent to the end of follow-up period. For this study, the follow-up period for recording of adverse events is defined as 2 weeks after the last dose of IMP or up to baseline/day 1 in the open-label safety extension study TV50717-CNS-30081 (whichever comes first) or 2 weeks after last site visit for patients who terminated early from the study.

All adverse events will be coded using MedDRA. Each patient will be counted only once in each preferred term or SOC category for the analyses of safety. Unless otherwise specified, adverse events will be summarized by SOC and preferred term, with SOCs and preferred terms within SOCs presented in descending order of patient incidence. Summaries will be presented for all adverse events (overall and by severity), adverse events determined by the investigator to be related to test IMP (ie, reasonable possibility; see Table 7 of the study protocol - defined as related or with missing relationship), overall and by severity, serious adverse events, and adverse events causing withdrawal from the study; Most common adverse events, defined as occurring in $> 4\%$ of the patients in either of the treatment groups overall, and by preferred term. Summaries will be presented by treatment group and for all patients.

Summaries will include treatment-emergent adverse events which are defined as adverse events occurring at or after the first dose of the IMP. The listings will include all adverse events recorded.

Patient listings of all adverse events, serious adverse events, adverse events leading to study drug discontinuation, adverse events leading to dose interruption and adverse events leading to death will be presented. Patient's dose at the time of the AE onset will be included in all listings.

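### Safety events and exposure from the first participation of re-entered patients reach listings but no summary table

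*SAP*

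**What the plan says.** Section 4.5 opens the re-entry route to a defined group: "Patients who terminate early from the study due to emergency circumstances", with COVID-19 as the example. It adds: "Patients re-entering the study will be manually assigned to their initial treatment group and will redo the entire study from the start".

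Section 3.3 defines the safety set: "The safety analysis set will include all randomized patients who receive at least 1 dose of IMP". For re-entrants it then restricts the data: "only the data from the repeated participation will be included in the safety analysis set". Section 4.5.3 repeats the restriction and says of the first participation: "The original participation data will be listed separately and will not be included in any summary tables". For an SAE in that period the rule is that, if it "resolved prior to re-entering, the SAE will be documented in medical history database".

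Section 8.1 runs the safety analyses on the safety set. Section 8.3 bases the adverse event summaries on "treatment-emergent adverse events which are defined as adverse events occurring at or after the first dose of the IMP" and makes no exception for re-entrants. Section 5.5 summarises medical history by system organ class and preferred term.

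**The concern.** A re-entrant who was dosed before leaving has two periods of exposure to the same assigned treatment, and the tables count only the second. A fresh start is a sound reason to base efficacy and change-from-baseline analyses on the repeated participation. It is not a reason to leave event counts and exposure out of the safety summaries.

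The rule also treats similar patients differently. A patient who leaves for an emergency reason and never returns keeps every event in the tables. A patient with the same record who does return loses the first-period events from them. Inclusion thus depends on something decided after dosing.

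Safety and tolerability are a stated secondary objective (Section 1.3). The comparison rests mainly on the incidence, SAE and exposure tables, and in a trial of about 65 patients a single patient is visible in them.

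**Working it through.** **Does any section return the first-participation data to a summary?** This is a question of reading, and the SAP states no figure to reproduce.

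- Section 3.3, general rule: one dose of study drug puts a randomised patient in the safety set. A re-entrant dosed in the first participation qualifies.
- Section 8.3: an event after the first dose is treatment-emergent. An event in the first participation after that dose qualifies.
- Sections 3.3 and 4.5.3, specific rule: the first participation is kept out of the safety set and out of all summary tables.
- Section 8.2: exposure is last day minus first day plus 1. Under the specific rule this covers the repeated participation only.
- Sections 5.5 and 8.3: the remaining outlets are the separate listing and, for a resolved SAE, the medical history record. Section 5.5 could then tabulate that SAE as history while the SAE table omits it.

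No section restores these events or days. A patient dosed in the first participation who returns but takes no dose meets the general rule, yet has no dosed data in the set. The text does not settle how that patient is counted.

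**Is the exclusion needed to keep the arms apart?** No. Section 4.5 returns re-entrants to their initial group, so first-period events can be attributed.

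**Size per affected patient.** Inputs: about 43 on TEV-50717 and about 22 on placebo (Section 2.4), and the threshold of more than 4% in either group for common events (Section 8.3).

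- TEV-50717: 1/43 = 2.3%. Restoring one patient to a term already seen once moves it from 1/43 = 2.3% (not common) to 2/43 = 4.7% (common).
- Placebo: 1/22 = 4.5%. Restoring one patient moves a term from 0/22 = 0% to 1/22 = 4.5% (common).

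These are maxima. Section 8.3 counts a patient once per term, so an event that recurs in the repeated participation changes nothing.

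**Chance that at least one SAE is left out.** The SAP gives neither the number of re-entrants, m, nor the first-period SAE risk, p. Both are assumed here for illustration, with patients independent. The chance is 1 − (1 − p)^m.

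| m | p = 2% | p = 5% | p = 10% |
|---|---|---|---|
| 1 | 2% | 5% | 10% |
| 3 | 6% | 14% | 27% |
| 5 | 10% | 23% | 41% |

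With m = 0 the chance is nil.

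**Exposure.** Let F1, L1 and F2, L2 be the first and last dosing days of the two participations. The exposure is (L1 − F1 + 1) + (L2 − F2 + 1). The Section 8.2 formula applied across the whole span would give L2 − F1 + 1. That is too long by F2 − L1 − 1 days, the off-drug gap.

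**The case against.** The rule is deliberate. It appears consistently in Sections 3.1, 3.3, 4.5.2 and 4.5.3, applies to both arms, and gives each patient one baseline, one titration and one set of analysis periods. A specific rule also ordinarily overrides a general definition. The data remain visible: they are listed, and the iDMC monitors safety on unblinded data throughout (Sections 2.2 and 2.3). The affected group is narrow and could be empty.

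Much of this stands, and it limits the point. Several stronger readings are tempting but unsupported:

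- A reader might infer that the data are discarded. They are kept out of the summaries and remain in a listing.
- A reader might infer that a first-period SAE is reclassified or deleted. Section 4.5.3 says only that a resolved SAE is documented in medical history. It does not say that the SAE record is removed, and it says nothing of an unresolved SAE. The fault is that the SAE summaries omit the event.
- A reader might infer that deaths or withdrawals for adverse events are lost. A patient who died cannot re-enter, and the route is for emergency terminations, not adverse events or tolerability.
- A reader might infer that first-exposure events are unlikely to recur, or that one omission would halve the SAE count. The SAP gives no recurrence rate and no expected number of SAEs.
- A reader might take every omitted event as an event on active drug. For placebo patients it is an event on placebo.

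What the objection does not answer is the gap in the tables. A listing does not correct an incidence or an exposure total, and the need for a single baseline applies to by-visit tables rather than event counts.

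**Conclusion.** The point holds as a should-fix. Followed as written, the SAP leaves out of all safety summaries any first-participation event that meets its own treatment-emergent definition, together with the matching exposure. Incidence could be understated if a re-entrant had an event that did not recur, and exposure if a re-entrant was dosed before leaving. Each such patient shifts a term by at most 2.3 percentage points on TEV-50717 or 4.5 on placebo, at the planned arm sizes, and that can decide whether a term is reported as common.

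The practical effect depends on the number of re-entrants, which the SAP does not give and which may be zero. The SAP does not support saying that the tables will be wrong, only that they could be incomplete.

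**What to change.** Amend Sections 3.3 and 4.5.3 as follows:

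- Include treatment-emergent adverse events, SAEs and potentially clinically significant values from both participations in the incidence summaries, under the treatment received, each patient counted once per term.
- Attribute each event to the treatment and follow-up period of the participation in which it occurred. Where a criterion needs a change from baseline, as in Table 6, use that participation's own baseline.
- Compute exposure as the sum of the two dosing intervals, excluding the off-drug gap, and note this in Section 8.2.
- State that a medical-history entry for the repeated participation does not replace the SAE in the SAE summaries.
- Keep by-visit and change-from-baseline tables on the repeated participation only.

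The cost is SAP wording and modest programming, since the plan already lists these data. Section 2.5.2 allows amendments up to database lock. The change does not touch the primary or key secondary analyses, which Section 2.5.1 freezes after the interim analysis.
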